Best Practice Alert (BPA) for Low Dose Aspirin Recommendation in High-Risk Pregnancies: a
Randomized Controlled Trial

Study Protocol with Statistical Analysis Plan

NCT05802940

06/05/2023

Study Protocol

Scientific Background

Preeclampsia is a significant cause of maternal morbidity and mortality, affecting up to 8% of pregnancies worldwide. Low dose aspirin (LDA) has been found to reduce the incidence of preeclampsia in high-risk pregnant patients.

Objectives

Upon internal review of electronic health record (EHR) data at our institution, we found that the recommendation for LDA use in high-risk pregnant patients was 60%. We hypothesize that the implementation of the EHR Best Practice Alert (BPA) will increase the healthcare provider's recommendation for LDA compared to the current standard care.

Design

We propose an RCT to assess the effect of an EHR clinical decision support (CDS) tool, specifically a BPA, on healthcare provider recommendations for low dose aspirin in high-risk pregnant patients.

Methods

Pregnant patients who receive and initiate prenatal care within Geisinger prior to 28 weeks gestation will be included if they are considered at high-risk of preeclampsia based on the modified United States Preventive Services Task Force (USPSTF) and American College of Obstetrics and Gynecology (ACOG) criteria listed above. Eligible patients will be randomized in a 1:1 fashion to a control or experimental group. In the control group, the women's health care provider will not receive a BPA; the pregnancy management will be based on the healthcare provider's current practice and knowledge. In the experimental group, the women's health care provider will receive a BPA in the EHR noting that the patient is at high-risk for preeclampsia and that the provider should recommend LDA. If LDA is not recommended, there will be a required acknowledgment reason from the provider noting a rationale for not initiating LDA. We defined women's health care provider as one of the following obstetric care providers who are able to prescribe medications: physicians (including resident physicians), physician assistants, certified registered nurse practitioners, and/or certified nurse midwives. Maternal-Fetal Medicine visits are excluded.

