In the experimental group, when the BPA fires, the provider can either accept the BPA recommendations (to prescribe LDA and to add this medication to the medication list) OR the provider can reject the BPA. If the BPA is rejected, the provider must choose a reason for rejection, i.e., patient declined, patient allergic to aspirin, patient taking aspirin, patient does not meet ACOG criteria for LDA, and Other (with comment). These specific rejection reasons will be reviewed by study team members on an on-going basis, so that the algorithm can be updated if needed to ensure it is only applying to those patients for whom LDA should be recommended.

Power Analysis

A total of 640 patients will be required to yield an adequate power to show a statistically significant difference in LDA recommendation rate. However, we plan to enroll an additional 10% to account for possible early miscarriages and early terminations.

Project Status

Patients will be randomized to study arms as they showed up to their appointments with an anticipated start date of June 19, 2023. Data collection is ongoing until the primary outcome date of June 19, 2025 (after the conclusion of pregnancy for all enrolled patients).

Statistical Analysis Plan

Planned Analyses

Primary Outcome: *A sensitivity analysis of the healthcare provider recommendation for low dose aspirin use in patients, specifically those who deliver after 28 weeks*
[Time Frame: Assessed between initial prenatal visit and delivery after 28 weeks]

Outcome Description: Patient chart indicates that the provider recommended aspirin (yes/no) between the day of the initial prenatal visit and delivery (≥ 28 weeks). The outcome is captured either by aspirin being added to the patient's medication record or via a prespecified algorithm searching notes for text strings such as "LDA," "ASA," "baby aspirin," etc. As per ACOG, low dose aspirin therapy should be initiated between 12 and 28 weeks, therefore we limited this outcome to patients who deliver after 28 weeks to ensure the provider had the entire window that ACOG allows to make the recommendation for low dose aspirin initiation.

Question: Does a BPA, which identifies patients as HRPP and recommends and facilitates LDA prescribing, that fires during prenatal visits increase the likelihood of LDA recommendation/prescribing in comparison with no BPA firing?

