Secondary Outcome: *The healthcare provider recommendation for low dose aspirin use in all randomized patients* [Time Frame: Assessed between initial prenatal visit and conclusion of pregnancy]

Outcome Description: Patient chart indicates that the provider recommended aspirin (yes/no) between the day of the initial prenatal visit and delivery (or conclusion of pregnancy). The outcome is captured either by aspirin being added to the patient's medication record or via a prespecified algorithm searching notes for text strings such as "LDA," "ASA," "baby aspirin," etc. This outcome will take into consideration all patients randomized, including those whose pregnancies resulted in termination, miscarriage or preterm delivery prior to 28 weeks. This intention-to-treat outcome will help assess the effect of the BPA in all patients.

Other pre-specified outcome measures

Outcome 1: *Patient taking low dose aspirin* [Time Frame: Assessed at time of delivery (≥ 28 weeks)]

Outcome Description: Patient chart indicates that the patient took aspirin (yes/no) during the pregnancy and up until delivery (≥ 28 weeks). The outcome is captured by aspirin being on the qualifying patient's medication record.

Outcome 2: *Rate of preeclampsia* [Time Frame: Assessed at time of delivery]

Outcome Description: Patient chart indicates that the patient experienced preeclampsia (yes/no) during the pregnancy, up until delivery. The outcome will be assessed at two time points, ≥ 28 weeks (so that patients were allowed the full window for low dose aspirin initiation) and ≥ 20 weeks (excluding miscarriages and earlier terminations of pregnancy). The outcome is captured by a diagnosis of preeclampsia on the qualifying patient's chart noted either by chart review or an algorithm that was created to capture this diagnosis.

Outcome 3: Timing of low dose aspirin recommendation [Assessed between initial prenatal visit to delivery (≥ 28 weeks)]

Outcome Description: Gestational age (in weeks) at the time that aspirin was first recommended (as indicated in the patient chart) between the day of the initial prenatal visit and delivery (≥ 28 weeks).

Outcome 4: Timing of low dose aspirin initiation [Assessed between initial prenatal visit to delivery (≥ 28 weeks)]

Outcome Description: Gestational age (in weeks) at the time that aspirin was initiated (as indicated in the patient chart) between the day of the initial prenatal visit and delivery (≥ 28 weeks)

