Outcome 5: Preterm delivery [Time Frame: Assessed at delivery]

Outcome Description: Patient chart indicates that the patient experienced a preterm delivery (yes/no) during the pregnancy. The outcome will be assessed at two time points, ≥ 28 weeks (so that patients were allowed the full window for low dose aspirin initiation) and ≥ 20 weeks (excluding miscarriages and earlier terminations of pregnancy). The outcome is captured by a diagnosis of preterm delivery on the qualifying patient's chart noted either by chart review or an algorithm that was created to capture this diagnosis.

Outcome 6: Provider response to best practice alert [Time Frame: Assessed between initiation prenatal visit to delivery (≥ 28 weeks)]

Outcome Description: Data from the best practice alert will inform the study team of which responses are selected by the provider when responding to the best practice alert. Selection of prespecified responses by the provider will be reviewed on a weekly basis during the study period to assess whether the best practice alert triggering criteria needs to be adjusted.

Outcome 7: Number of times the best practice alert fired for a patient [Time Frame: Assessed between initial prenatal visit to delivery (≥ 28 weeks)]

Outcome Description: The BPA will stop firing once the BPA has been successfully addressed. Data from the BPA will inform the study team the number of times the BPA fired for a qualifying patient.

Analysis Notes

Recent work suggests that OLS regressions are appropriate in randomized experiments with binary outcome variables such as ours (Gomila, 2021).

Each analysis for the specified outcomes will be run using an OLS regression to examine whether the outcome differs as a function of experimental arm. For all analyses, if the distribution for a continuous outcome is positively skewed, a negative binomial or other appropriate model may be used instead.

As the treatment variation is at the individual level, we will report heteroskedasticity-robust standard errors. We will also explore the impact of clustering these standard errors at the clinic and clinic-date levels to allow for dependence across observations within these clusters. We will also investigate heterogeneity across clinics that vary along characteristics of interest, including prior-year recommendation rates.

References:

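### Outcomes 3 and 4 (week of first aspirin recommendation or initiation) have values only for recipients, so OLS on arm compares self-selected subsets and does not isolate the BPA's effect on timing

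*Combined protocol and SAP*

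**What the plan says.** Under the other pre-specified outcome measures, Outcome 3 is "Gestational age (in weeks) at the time that aspirin was first recommended" and Outcome 4 is "Gestational age (in weeks) at the time that aspirin was initiated". Both are limited to patients who deliver at 28 weeks or later.

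The Analysis Notes apply one method to everything: "Each analysis for the specified outcomes will be run using an OLS regression to examine whether the outcome differs" by arm. The only departure allowed is for skew: "if the distribution for a continuous outcome is positively skewed, a negative binomial or other appropriate model may be used instead". Standard errors are to be heteroskedasticity-robust, with clustering explored.

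Two other statements bear on the point. The Objectives report an internal review: "we found that the recommendation for LDA use in high-risk pregnant patients was 60" per cent. The question under the Primary Outcome asks whether the BPA will "increase the likelihood of LDA recommendation/prescribing in comparison with no BPA firing".

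Nowhere does the plan define an analysis set, an assigned value, a censoring rule or a descriptive label for patients who are never recommended or never start aspirin.

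**The concern.** A gestational age at recommendation does not exist for a patient who was never recommended aspirin, and OLS cannot use an undefined value. Followed as written, the plan therefore drops those patients. Being recommended happens after randomisation, and it is the very thing the BPA is meant to change. If the trial succeeds on its primary outcome, the recipients in the two arms are no longer comparable. The BPA arm then contains the kind of patient who is recommended anyway, plus patients recommended only because the alert fired.

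The difference in mean week then mixes two things: any change in timing for patients recommended in either arm, and the timing of the added patients. A false effect on timing could appear, or a real one could be hidden or exaggerated. A reader who sees a by-arm regression in a randomised trial would naturally take the result as the BPA's effect on timing.

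**Working it through.** **What the plan's own figures give.** The plan states no figure for timing. Its 60% rate leaves 100% - 60% = 40% of controls without an Outcome 3 value. No initiation rate is given, so the corresponding share for Outcome 4 cannot be computed.

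**Inputs.** From the documents: 60% recommended under usual care, 1:1 allocation, and a total of 640, hence 320 per arm. The Power Analysis gives no target rate, significance level or power, so 640 cannot be reproduced. It is used here only to set the number per arm.

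Assumed, because the documents are silent:
- BPA-arm rate pE of 72%, with 66% and 80% as alternatives. For scale, 60% vs 72% at two-sided 5% and 90% power needs 652, and 60% vs 70.5% at 80% power needs 644; both are close to 640.
- Patients recommended under usual care: mean 12.5 weeks, SD 3.
- BPA-only recommendations: mean m weeks, SD 4.
- Everyone recommended under usual care would also be recommended under the BPA.
- Two-sided 5% test.

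**Who is compared.** Controls: 0.60 x 320 = 192. BPA arm: 0.72 x 320 = about 230. The share of BPA recipients with no counterpart among control recipients is (pE - 0.60)/pE: 9% at 66%, 17% at 72%, 25% at 80%.

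**Expected OLS contrast.** With a true timing shift s in patients recommended in either arm:

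contrast = [0.60 x (12.5 + s) + (pE - 0.60) x m]/pE - 12.5

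At pE = 0.72 and s = 0 this reduces to (m - 12.5)/6. Rejection probabilities come from 6,000 simulated trials per row, OLS with robust standard errors.

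| m (weeks) | Contrast, s = 0 | P(significantly later) | Contrast, s = -0.5 | P(significantly later) |
|---|---|---|---|---|
| 10.5 | -0.33 | 0.001 | -0.75 | 0.000 |
| 12.5 | 0 | 0.029 | -0.42 | 0.000 |
| 14 | +0.25 | 0.135 | -0.17 | 0.006 |
| 15 | +0.42 | 0.274 | 0 | 0.027 |
| 16 | +0.58 | 0.456 | +0.17 | 0.079 |
| 18 | +0.92 | 0.798 | +0.50 | 0.328 |

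At m = 10.5 and s = 0, the result is significantly earlier in 19% of trials.

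**Sensitivity to the BPA rate.** At m = 18 and s = 0: (0.06/0.66) x 5.5 = +0.50 at 66%, and (0.20/0.80) x 5.5 = +1.38 at 80%.

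**When the sign reverses.** For s = -0.5, the contrast is zero at m = 12.5 + 0.30/(pE - 0.60). That is 17.5 weeks at 66%, 15.0 at 72% and 14.0 at 80%. Above these values a real shift to earlier recommendation would appear as later.

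**A second set of assumptions.** With mean 13 and SD 3 throughout, a 70% BPA rate and s = 0, the contrast is -0.29, 0, +0.43 and +1.00 week for added means of 11, 13, 16 and 20 weeks. The nominal 5% test rejects in 15%, 5%, 28% and 85% of trials. The pattern is the same.

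**The skew clause.** It is triggered by the shape of the distribution, not by undefined values. A negative binomial model, or any other model of the same values, would be fitted to the same selected patients. Robust or clustered standard errors change the stated precision, not who is compared.

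**The case against.** The strongest reply concerns weight. Outcomes 3 and 4 are in the lowest tier, no trial conclusion depends on them, and the plan never claims that the contrast isolates an effect on timing. Mean week among recipients is a legitimate description. That non-recipients are dropped is inferred from the definitions; the plan does not say so. All this is fair and limits the priority. But the plan commits both outcomes to a by-arm regression without labelling it descriptive, so the flaw is in the stated analysis and is more than a missing detail.

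The magnitude rests on assumptions. The largest figures need BPA-only recommendations to average 5.5 weeks later than the others, which nothing in the documents supports, and near the control mean the bias vanishes. The 60% comes from an internal review not described as covering deliveries at 28 weeks or later. Since patients, not providers, are randomised, spill-over could raise the control rate. If it rose to 66% with the BPA arm at 72%, the m = 18 figure would fall to (0.06/0.72) x 5.5 = +0.46. These points stand as limits on size; they do not make the groups comparable.

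The remedy can also be faulted. A proportion recommended by a given week is not a pure timing measure and overlaps with the primary outcome. This stands and must be disclosed. Patients may enter care at any time before 28 weeks, so someone first seen after the chosen week counts as not recommended. That applies to both randomised arms alike and dilutes the contrast without biasing it. Stopping the curve at 28 weeks leaves out later recommendations, but the primary yes/no outcome counts those.

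**Conclusion.** The concern holds. The planned by-arm OLS for Outcomes 3 and 4 is not a comparison of randomised groups, and it cannot be read as the BPA's effect on when aspirin is recommended or started. That conclusion rests only on the outcome definitions, the blanket OLS rule, the 60% rate and the trial's own hypothesis.

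The size does depend on assumptions. At a 72% BPA rate with no true timing change, the spurious difference runs from -0.33 to +0.92 week as BPA-only recommendations average 10.5 to 18 weeks. It is zero if they come, on average, when the others do. The direction cannot be known in advance. The yes/no primary and secondary outcomes are untouched, so this should be corrected but does not threaten the main result.

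**What to change.** In the SAP, for Outcomes 3 and 4:

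1. Keep the plan's population (delivery at 28 weeks or later) and keep all of these patients in the denominator, including those never recommended or never started. This retains the plan's own post-randomisation restriction, which the SAP should acknowledge.
2. Compare by arm the proportion first recommended (Outcome 3) or started (Outcome 4) by gestational weeks fixed in advance within the plan's 12-28-week window, using the same OLS with robust standard errors.
3. Show cumulative incidence by arm up to 28 weeks. In this population the end of pregnancy cannot intervene before then. If all randomised patients are added as a supplement, say that the population changes and treat the end of pregnancy as a competing event.
4. Report mean gestational age among recipients descriptively, with the number of recipients per arm and no causal comparison.

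The cost is SAP wording and a little extra analysis on the same chart dates. The price in interpretation should be stated: the new measure combines how often and how early aspirin is recommended. Under the inputs above with no timing change, and m from 10.5 to 18, the proportion by week 16 is 52.7% vs 56.4-63.7% (+3.7 to +11.0 points). By week 20 it is 59.6% vs 67.9-71.5% (+8.3 to +11.9 points). Those differences come wholly from added recommendations. Weeks 16 and 20 are illustrations, not proposals.

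A separate drafting point, which adds no weight here: Outcomes 6 and 7 should be exempt from the by-arm rule and described in the experimental arm only, since no alert fires in controls.

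### The recommendation outcomes are compared by arm alone; prespecifying two baseline covariates would be an optional, nearly free and probably small precision gain

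*Combined protocol and SAP*

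**What the plan says.** The Analysis Notes give one model for all outcomes: OLS "to examine whether the outcome differs as a function of experimental arm". On uncertainty they state: "As the treatment variation is at the individual level, we will report heteroskedasticity-robust standard errors". Clustering by clinic and by clinic-date is to be explored as well. No baseline covariate is named for any model. The plan is silent on adjustment and does not rule it out.

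Two candidate covariates can be found in the documents:

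- **Clinic prior-year recommendation rate.** It appears only in the Analysis Notes, for a different purpose: "We will also investigate heterogeneity across clinics that vary along characteristics of interest, including prior-year recommendation rates".
- **Gestational age.** Methods needs it for eligibility: "Pregnant patients who receive and initiate prenatal care within Geisinger prior to 28 weeks gestation will be included". Project Status adds: "Patients will be randomized to study arms as they showed up to their appointments". Gestational age on that day should therefore be obtainable. The SAP uses it only as an outcome scale (Outcomes 3 and 4) and to define delivery windows.

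No stratification of the randomisation is described.

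**The concern.** The plan treats recommendation as something that may differ between clinics: it proposes clinic-level clustering and a look at clinics by prior-year rate. It also ties recommendation to a gestational window of 12 to 28 weeks, so a patient who enters late has less of that window left. Both variables are fixed before assignment and either could predict the outcome, yet neither enters the main comparison.

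Prespecified baseline covariates leave the randomised arm effect essentially unbiased. They can narrow its interval and correct for chance imbalance between high- and low-recommending clinics. Clustered standard errors do not remove such an imbalance from the estimate. If covariates were chosen only after the data had been seen, the choice would be open to question, which is the reason to settle it in the SAP. What is at stake is some precision on the two recommendation outcomes; the validity of the result is not in doubt.

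**Working it through.** **Inputs from the documents.** Current recommendation rate 60% (Objectives); 1:1 allocation (Methods); 640 patients (Power Analysis), hence 320 per arm.

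**Assumed inputs.** Target rate 70%; two-sided alpha 0.05; between-clinic SD of 5, 10 or 15 points; 10 to 40 clinics; prior-year rate based on 60 patients per clinic.

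The figure of 640 cannot be reproduced, because the target rate, alpha, sidedness and power are not stated. For orientation, 60% vs 70.5% at two-sided 0.05 and 80% power needs 644, while 60% vs 70% needs 712. The 70% target is therefore only illustrative.

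**1. Arm only.** SE = √[(0.60×0.40 + 0.70×0.30)/320] = √(0.45/320) = 0.0375. Power = Φ(0.10/0.0375 − 1.96) = Φ(0.707) = 0.760.

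**2. What a clinic rate can explain.** If the true clinic rate were known, R² ≈ SD²/0.24, which is 0.0104, 0.0417 and 0.0938 at SDs of 5, 10 and 15 points. A rate estimated from 60 patients is noisy, with sampling variance of about 0.24/60 = 0.004. At SD 10 its reliability is 0.010/(0.010 + 0.004) = 0.714, so usable R² ≈ 0.0417 × 0.714 = 0.030. The SE falls by 1 − √(1 − 0.030) = 1.5%.

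**3. Simulation with the prior-year rate as the only covariate.** N = 640, 60% vs 70%, robust (HC1) errors, 5,000 runs per setting, 10 or 40 clinics. The ranges for cases 1 and 2 also include a smaller set of 1,500 runs at 60% vs 70.6%. Each cell gives the fall in SE, then the power from the step 1 formula with the SE multiplied by (1 − fall).

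| Case | SD 5 | SD 10 | SD 15 |
|---|---|---|---|
| 1. Rate from 60 patients per clinic | 0.1–0.2%; 0.761–0.762 | 1.5%; 0.772–0.773 | 3.7–4.1%; 0.791–0.794 |
| 2. As 1, alert halves clinic differences in the treated arm | ≤0.1%; 0.760–0.761 | 0.8%; 0.767 | 2.1–2.3%; 0.778–0.779 |
| 3. As 1, prior-year rate defined differently (correlation 0.7 with the trial-definition rate) | ≤0.1%; 0.760–0.761 | 0.7–0.8%; 0.766–0.767 | 2.0–2.1%; about 0.777 |
| 4. Both 2 and 3 | 0%; 0.760 | 0.4%; 0.763–0.764 | 1.1–1.2%; 0.769–0.770 |

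With only 20 patients behind each clinic's rate, the fall at SD 10 drops to 0.98%, or to about 0.5% if the alert also halves clinic differences.

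**4. In patients.** Effective N = 640/(1 − fall)². At SD 10:

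- case 1: 640/0.985² = 660, about 20 patients
- case 2: 640/0.992² = 650, about 10 patients
- case 4: 640/0.996² = 645, about 5 patients

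**5. Gestational age.** The documents give no effect size. As an illustration, a separate simulation (20 clinics, rate from 100 patients per clinic, entry at 6 to 27.9 weeks, HC2 errors, 4,000 runs) included both covariates and varied the gestational-age slope:

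- SD 5, 0.5 points per week: SE falls 0.3%
- SD 10, no slope: 1.6%
- SD 10, 1 point per week: 2.5%
- SD 15, 1 point per week: 5.0%
- SD 15, 2 points per week: 7.4%

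**6. Cost and validity.** If neither covariate predicts the outcome, the two lost degrees of freedom raise the SE by √(638/636) − 1 = 0.16%. Simulation gives 0.15 to 0.16%, and power at 0.15% is 0.759. In the step 3 settings the mean arm effect moved by less than 0.0002. With no true effect (SD 10, 1 point per week), rejection was 4.6% both with and without adjustment.

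**The case against.** The strongest reply is that nothing is broken. The arm-only estimate is unbiased, its errors are robust, and the plan does not promise adjustment anywhere. The benefit depends on a clinic SD, a number of clinics and a gestational-age effect that the documents do not give. That is correct, and it is why the point is only an optional refinement.

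Several narrower points also stand:

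- Gestational age has no supporting figure. The eligibility rule concerns when care begins, whereas the covariate is measured on the randomisation day, which need not be the first visit. A linear term may also fit a 12-to-28-week window poorly. A poor fit would reduce the gain but would not bias the arm effect under randomisation.
- The alert may well compress clinic differences in the treated arm, so cases 2 and 4 deserve as much weight as case 1.
- Recommendation can occur at any visit up to delivery, so the randomising clinic is an imperfect proxy. That dilution was not modelled.
- The 70% target is not the trial's. At 72.1%, where arm-only power is about 0.90, a 1.5% fall in SE adds only about 0.8 power points. The secondary outcome covers all randomised patients. With 640 + 64 = 704, or 352 per arm, arm-only power at 60% vs 70% is already about 0.80.
- Rebuilding the prior-year rate to the trial's definition could mean running the note search on a year of historical charts. Without the rebuild, cases 3 and 4 apply.

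These points reduce the size of the gain. They do not reverse its direction or make the adjusted analysis unsound.

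**Conclusion.** The point holds as an optional improvement. The arm-only model is valid, but it leaves unused two pre-randomisation variables that the team should have.

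On the assumed 320 per arm, 60% vs 70% and two-sided 0.05, the prior-year rate adds between 0 and 1.3 power points (0.760 to at most 0.773) at clinic SDs of 5 to 10 points. At an SD of 15 it adds between 0.9 and 3.4 points (0.769 to 0.794). The gestational-age gain is unknown. The worst outcome found is an SE about 0.15% larger. The clinic SD, number of clinics, target rate and alpha are all assumptions. The documents also do not say whether the prior-year rate uses the trial's high-risk criteria and outcome capture, nor how well either variable predicts recommendation.

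**What to change.** For the primary and secondary recommendation outcomes only, prespecify OLS on:

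- arm;
- the prior-year recommendation rate of the clinic where the patient was randomised;
- gestational age in weeks on the day of randomisation.

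Keep the planned robust standard errors and report the unadjusted difference alongside. Where possible, compute the prior-year rate with the trial's own high-risk criteria and its outcome capture, "either by aspirin being added to the patient's medication record or via a prespecified algorithm searching notes"; otherwise state the definition used. Give a clinic without a prior-year rate the overall mean. Leave Outcomes 1 to 7 as planned.

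The cost is one or two SAP sentences, slight extra analysis work and no new patients. It is higher if the prior-year rate has to be rebuilt to the trial's definition. The gain may prove negligible.
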